8. STUDY VARIABLES

8.1 Demographic and Baseline Characteristics

Baseline characteristics will include standard demography (e.g. age, race, weight, height, etc.), disease characteristics including medical history, and medication history for each patient.

8.2 Primary and Secondary Endpoints

Primary Endpoints

Effect of dexamethasone insert through Day 90 as measured by -

- 1. Mean Reduction in IOP at 1 and 3 months as measured by Goldmann Applanation Tonometer and comparison between groups
- 2. Mean change in ETDRS BCVA at 1 and 3 months and comparison between groups
- 3. Difference in adverse events between the two groups
- 4. Difference in number of glaucoma medications between the wo groups at 3 months

Secondary Endpoints

Through Day 90 as measured by -

- 1. Number of patients requiring supplemental prednisolone acetate 1% eye drops
- 2. Incidence of CME at 90 days as seen on OCT

- 3. Difference in Ocular Comfort Index between the two groups at 1 month and 3 months
- 4. Difference in percentage of patients with absence of anterior chamber cells at 30 days between groups

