Clinical Study Protocol

ProSpective StUdy on DEXTENZA® SafeTy And EffIcacy following coNcomitant MIGS and Cataract Surgery

The SUSTAIN Study

Compound: Sustained Release Dexamethasone,

0.4 mg

IND Number: 146602

NCT: 04200651

Study Name: Prospective Study on DEXTENZA®

Safety and Efficacy following concomitant MIGS and Cataract

Surgery

Clinical Phase: Phase IV open label prospective

Date of Issue: 10/18/2020

Primary Investigator: [name]

Sub Investigator: [name]

Site Name & Location: New York Eye Surgery Center, [name]

CLINICAL STUDY PROT	OCOL SYNOPSIS					
TITLE	Prospective Study on DEXTENZA® Safety and Efficacy following concomitant MIGS and Cataract Surgery					
SITE LOCATION(S)	New York Eye Surgery Center, [name]					
PRINCIPAL	[name]					
Investigator						
Objective(s)	To compare dexamethasone insert to topical corticosteroid use through 90 days in glaucomatous eyes undergoing MIGS and cataract surgery as measured by: visual acuity, IOP control, adverse events, control of inflammation, macular health, and patient comfort.					
STUDY DESIGN	Prospective Fellow-Eye, Randomized Open-label Interventional Study					
STUDY DURATION	Fourteen months, including enrollment period					
ESTIMATED STUDY COMPLETION DATE	February 2022					
POPULATION Sample Size: Target Population:	40 eyes Patients with cataract and glaucoma					
TREATMENT(S) Study Drug	Sustained Release Dexamethasone, 0.4 mg					
Dose/Route/Schedule:	All study eyes will receive cataract extraction, IOL placement, minimally-invasive glaucoma surgery, and a postoperative topical antibiotic prescription. 20 eyes will be randomized to receive Sustained Released Dexamethasone, 0.4 mg. 20 eyes will be prescribed a prednisolone acetate 1% regimen.					
ENDPOINT(S)						
Primary:	 Reduction in IOP at 1 and 3 months BCVA at 1 and 3 months Difference in adverse events between groups Difference in # of glaucoma meds at 3 months 					
Secondary:	 Number of patients requiring supplemental prednisolone acetate 1% eye drops Incidence of CME at 90 days as seen on OCT Difference in Ocular Comfort Index between groups at 1 month and 3 months Difference in % of patients with absence of 					

anterior chamber cells at 30 days between groups

TABLE OF CONTENTS

Clir	nical Stu	dy Protocol Synopsis	2
List	of Table	es	4
1.	Introdu	ction	5
1.1	Type	of study	5
1.2	Introd	luction	5
1.3	Ratio	nale	5
1.4	Purpo	se	6

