In terms of primary study endpoints, change in IOP values at 1 and 3 months are crucial for quantifying glaucoma outcome differences between groups. We will use three methods to comprehensively assess IOP changes, including Goldmann applanation tonometry, CATS tonometer prism, and the automatic IOP readings provided by the ocular response analyzer. Goldmann is the current standard of care, and thus will be the primary measure. However, CATS tonometry is a valuable supplement because it utilizes a modified prism that may better account for central corneal thickness and corneal hysteresis when providing IOP measurements (McCaffertey et al. 2019). Change in number of glaucoma medications from preop to 3 months postop will be serve as an additional metric to compare glaucoma outcomes. BCVA measurements using an ETDRS chart at 4 meters will indicate whether DEXTENZA® placement in this population affects the visual acuity improvement conferred by an IOL and MIGS. Recording adverse events is necessary not only for the integrity of the study, but also for evaluating the safety of the DEXTENZA® insert for this study population.

supplementary prednisolone acetate 1% eye drops will be recorded to compare ocular inflammation between groups. Checking for absence of anterior chamber cells at 30 days will provide another measure of control of inflammation. Incidence of cystoid macular edema at three months will be used to compare macular health between groups.

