9. STATISTICAL PLAN

Primary endpoints and secondary endpoints will be analyzed through statistical hypothesis testing. Demographic and baseline characteristics will be summarized descriptively. Continuous variables will be summarized with mean, median, and standard deviation. Categorical variables will be summarized with frequency and percentage.

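### The plan calls for no adjustment for the preop value or MIGS type when comparing IOP, BCVA and glaucoma medications, and it defines the medication endpoint in two ways

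*Combined protocol and SAP*

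**What the plan says.** Section 8.2 lists the three quantitative primary endpoints as follows:

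- IOP: "Mean Reduction in IOP at 1 and 3 months as measured by Goldmann Applanation Tonometer and comparison between groups".
- BCVA: "Mean change in ETDRS BCVA at 1 and 3 months and comparison between groups".
- Glaucoma medications: "Difference in number of glaucoma medications between the wo groups at 3 months". The synopsis agrees: "Difference in # of glaucoma meds at 3 months". Section 1.5 instead describes the metric as "Change in number of glaucoma medications from preop to 3 months postop".

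The analysis text is in Section 9. On inference it says "Primary endpoints and secondary endpoints will be analyzed through statistical hypothesis testing", and on baseline data "Demographic and baseline characteristics will be summarized descriptively". It names no test, model, covariate, stratum term or paired method.

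Table 1 in Section 5.1 schedules IOP, BCVA and concomitant medications (including glaucoma medications) at screening/baseline. Section 5.2.1 lists four MIGS types. Section 3.1 randomises single-eye patients in blocks within MIGS type, on the stated ground that the device may confound outcomes such as IOP. In the few patients who enrol both eyes, each eye has the same MIGS procedure and the two eyes go to opposite arms. Section 1.5 sets 40 eyes, 20 per arm.

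**The concern.** The design collects the strongest likely predictor of each outcome, the eye's own preop value, and it stratifies on a factor that it says can affect IOP. The analysis text then commits to using neither as a model term. For IOP and BCVA the preop value enters only by subtraction, which is efficient only under particular variances and correlations. For medications, as Section 8.2 words the endpoint, the preop count does not enter at all, while Section 1.5 subtracts it. An analyst could therefore choose among the change, the 3-month value and the adjusted comparison after seeing the data.

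Precision is scarce at 20 eyes per arm. Section 1.3 says the study is meant to answer surgeons' concern about raised IOP with the insert. In that setting an avoidably wide interval, or a test that runs below its nominal level, makes a real difference easier to miss, and the result could be read as reassurance.

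**Working it through.** **The plan's own figure.** The 40 eyes cannot be reproduced, because the documents give no alpha, power, effect size, SD or margin. From the documents come 20 eyes per arm, four MIGS types and few two-eye patients. Everything else below is assumed and shown over a range.

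**1. Preop adjustment, equal variances.** Let ρ be the preop-postop correlation. In units of the outcome variance, the variance factors are 1 for the 3-month value, 2(1 − ρ) for the change and 1 − ρ² for the adjusted comparison. The cut in standard error (SE) is therefore

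- against the change: 1 − √((1 + ρ)/2)
- against the 3-month value: 1 − √(1 − ρ²)

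| ρ | Cut vs change | Cut vs 3-month value |
|---|---|---|
| 0.3 | 19.4% | 4.6% |
| 0.5 | 13.4% | 13.4% |
| 0.7 | 7.8% | 28.6% |

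For scale, the difference detectable with 80% power at two-sided 5% is about (1.960 + 0.842) × √(2/20 × factor), in SD units:

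| ρ | 3-month value | Change | Adjusted |
|---|---|---|---|
| 0.3 | 0.886 | 1.048 | 0.845 |
| 0.5 | 0.886 | 0.886 | 0.767 |
| 0.7 | 0.886 | 0.686 | 0.633 |

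**2. Unequal variances.** Let k be postop SD divided by preop SD. The variance of the change is 1 + k² − 2ρk, and the adjusted variance is k²(1 − ρ²). At ρ = 0.5:

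- k = 0.7: 0.3675/0.79 = 0.465, a cut of 32%
- k = 1: 0.75/1 = 0.75, a cut of 13%
- k = 1.5: 1.6875/1.75 = 0.964, a cut of 2%
- k = 2: 3/3 = 1, no cut

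**3. Check at 40 eyes.** A simulation with MIGS terms in the model used 2 to 6 pairs, between-eye correlations of 0.3 to 0.7, MIGS shares of 40/30/20/10% and blocks of 4 (all assumed). At ρ = 0.3, 0.5 and 0.7, the cuts against the change were 17.8–18.6%, 11.8–12.5% and 6.2–6.6%. Against the 3-month value they were 2.7–3.3%, 11.3–11.9% and 27.0–27.6%. The latter gain shrinks if fellow eyes also correlate strongly across time: with that correlation at 0.48, ρ = 0.5 and a between-eye correlation of 0.5, it was 10% with 3 pairs and 7% with 6.

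**4. MIGS type.** If device explains a share R² of outcome variance and randomisation balances it, a test that omits it has a true level near 2(1 − Φ(1.960/√(1 − R²))). That is 3.9%, 2.8% and 1.9% for R² = 0.1, 0.2 and 0.3. In simulation with 3 pairs at between-eye correlation 0.5, pairs also ignored, the level was 3.2%, 2.3% and 1.5% without MIGS terms and 4.2%, 4.0% and 3.8% with them. The true SE hardly moved: 0.257, 0.246 and 0.235 without, against 0.257, 0.245 and 0.232 with.

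**5. Pairs.** With m opposite-arm pairs and between-eye correlation r, the reported SE divided by the true SE is 1/√(1 − m·r/20). For m = 3 and r = 0.5 this is 1/√0.925 = 1.040. It runs from 1.015 (m = 2, r = 0.3) to 1.125 (m = 6, r = 0.7).

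**6. Cost in degrees of freedom.** The preop value plus three MIGS terms takes residual degrees of freedom from 38 to 34, and the critical t from 2.024 to 2.032.

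**The case against.** The strongest reply is that Section 9 is silent and does not choose an inferior method. It names no test, so an unadjusted t-test on changes is a comparator supplied by the review, and adjustment remains open. Under randomisation the change score, the 3-month value and the adjusted comparison are all unbiased, so the issue is efficiency. This stands, and it limits the point to a recommended improvement.

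Several stronger readings are tempting, but the documents do not support them:

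- A reader might infer that the preop value is left out altogether. For IOP and BCVA it is already in the endpoint by subtraction. Only the medication endpoint as worded in Section 8.2 omits it.
- A reader might infer that Section 9 limits baseline data to description. That sentence concerns demographic and baseline characteristics, which Section 8.1 describes as demography, disease characteristics and medication history. It does not restrict how preop IOP or BCVA may be used.
- A reader might infer that ignoring strata or pairs raises the false-positive rate. Steps 4 and 5 show the opposite: both omissions are conservative.
- A reader might see a second conflict in the synopsis entry "BCVA at 1 and 3 months". It reads as shorthand for the fuller definition in Section 8.2.

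It also stands that the gain from modelling pairs is small when they are few, that MIGS terms correct the error bars and add almost no true precision, and that the 8% to 19% range against a change score depends on equal variances.

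**Conclusion.** The point holds as a free improvement. The plan leaves unprespecified a method that, in large samples with few pairs, is never less precise than either comparison it lists, and it gives two definitions of the medication endpoint that must be reconciled.

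The preop adjustment carries most of the benefit, because it applies to every eye. Its size rests on assumed correlations and variance ratios. Against a change score at ρ = 0.5 it could be anything from about a third off the standard error to nothing. The figures are for a continuous outcome and are only indicative for the medication count. Adding MIGS type brings the test closer to its nominal level. Allowing for pairs matters least: at 3 pairs and a between-eye correlation of 0.5, the standard error is about 4% too large if they are ignored. Nothing here suggests bias or excess false positives in an unadjusted analysis.

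**What to change.** In Section 9, state that IOP and BCVA at 1 and 3 months, and medication number at 3 months, will be analysed by eye with treatment, the preop value and MIGS type in the model. Use the MIGS type determined before the envelope was opened, and pool rare types by a rule fixed in advance.

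Give the medication endpoint one definition in the synopsis, Section 1.5 and Section 8.2: the 3-month difference adjusted for the preop count. In a linear model this also settles the choice between change and follow-up value. If Y − X = a + bT + cX, then Y = a + bT + (c + 1)X, so the treatment estimate b is the same either way. This identity does not carry over to a count or ordinal model.

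For the few two-eye patients, use a method that respects the pairs and is valid at this size, such as a re-randomisation test that follows the strata and pairs. In simulation under assumed block sizes of 2, 4 and 6, its level was 4.1% to 5.8%. Do not use a random-patient model with residual degrees of freedom, which ran at 9.4% to 12.9%.

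The cost is about 4 degrees of freedom, a pooling rule, one reconciled definition and a short script, which needs the block size from the randomisation schedule. No new visit or measurement is required.

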1.3 Rationale

Glaucoma and cataract surgery patients face an outsize postoperative burden. In addition to taking frequent anti-inflammatory eye drops, they often continue their glaucoma medications. This can cause patient confusion and nonadherence, potentially leading to poor healing, slower recovery period, and/or cystoid macular edema. DEXTENZA®, as a sustained release anti-inflammatory insert, could help preclude adherence difficulties and increase comfort by reducing eye drop load. However, glaucoma surgeons may hesitate to adopt DEXTENZA® due to concerns regarding safety with respect to elevated intraocular pressure. This prospective study will address those concerns directly, providing timely and high-quality clinical evidence comparing DEXTENZA® to standard-of-care steroid eye drops. For physicians and patients, the results of this study will prove immediately useful for therapeutic decision-making.

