3. STUDY DESIGN

3.1 Study Description and Duration

This prospective, open-label, single-center, randomized, fellow-eye, October 18, 2020 Page 7

investigator-initiated clinical study seeks to investigate the safety and efficacy of the dexamethasone insert in glaucoma patients after concomitant MIGS and cataract surgery. After screening a given patient for inclusion and exclusion criteria, and gaining informed consent, the patient's eligible eye will be randomized to either receive the dexamethasone insert after concomitant cataract-MIGS or to receive prednisolone acetate 1% eye drops after concomitant cataract-MIGS. For participants who enroll only a single eye, block randomization will be performed to ensure that the type of MIGS surgeries will be balanced between the two treatment groups. This stratification is necessary because it is possible that different MIGS devices can confound endpoint measurements, such as IOP control. A stratified block randomization schedule will be developed in advance by the sub-investigator through a computer program, and each assignment will be placed in opaque, sealed envelopes that will be labeled with the stratifying MIGS category. The primary investigator will only open an envelope after a patient is enrolled and the MIGS type that is suitable for the patient is determined. In the few cases where a patient enrolls both eyes, the same MIGS surgery will be performed for each eye. Under such a circumstance, simple randomization will be sufficient to determine whether the first or second eye operated on will receive the dexamethasone insert. The other eye will be placed in the prednisolone acetate 1% eye drops group.

Per enrolled eye, the study period will last for approximately 90 days after surgery, consisting of four postop follow-up visits. At Day 1, Day 7, Day 30, and Day 90, primary and secondary endpoints will be assessed alongside standard-of-care procedures. Adjusting for enrollment period, the study will last a total of approximately twelve months.

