4.2 Treatment Logistics and Accountability

4.2.1 Packaging, Labeling, and Storage

Intracanalicular dexamethasone insert must be stored in a secure area accessible only to the Investigator and their designee(s) and refrigerated and stored between 2° C and 8° C. Intracanalicular dexamethasone insert contains 0.4 mg dexamethasone and is designed to provide a sustained and tapered release of therapeutic levels of dexamethasone to the ocular surface for up to 30 days for the reduction of post-surgical inflammation and pain associated with ocular surgery. Dexamethasone is an anti-inflammatory 9-fluoro-glucocorticoid (also termed a glucocorticoid agonist) and is the active ingredient found in MAXIDEX® 0.1% (dexamethasone ophthalmic suspension), which contains approximately 50 µg of dexamethasone per drop.

Study inserts will be supplied by Ocular Therapeutix in a sealed foil pouch containing one intracanalicular dexamethasone insert in a foam carrier.

Study inserts will be shipped to the site via overnight shipping using cold packs to maintain a temperature of 2° to 8° C. The Investigator, or an approved representative (e.g. pharmacist), will ensure that all study drug inserts are stored in a secured area, under recommended storage conditions and in accordance with applicable regulatory requirements. The shipping box is to be opened and stored immediately at the site in a refrigerator intended

for investigational products at a temperature of 2° to 8°C.

When the insert is removed from the refrigerator, it should be visually inspected. Exposure of the insert to temperatures outside these limits it not recommended. Records of actual storage conditions (i.e. temperature log) at the study site must be maintained; and must include a record of the dates, when the refrigerator was checked, the initials of person checking, and the temperature.

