5. STUDY SCHEDULE OF EVENTS AND VISIT DESCRIPTIONS

5.1 Schedule of Events

Study assessments and procedures are presented by visit in Table 1.

 Table 1
 Schedule of Events

Study Procedure	Screening/ Baseline	Surgica l Visit Day 0	Day 1	Day 7	Day 30	3 MTH post-op	Early Termi nation
Visit	VISIT 1	VISIT 2	VISIT 3	VISIT 4	VISIT 5	VISIT 6	
Windows for Visits	(Day -90 to - 1)		(+/- 2 days)	(+/- 2 days)	(+/- 7 days)	(+/- 14 days)	
Inclusion/Exclusion	X						
Informed Consent	X						
Demographics	X						
Medical History and Concurrent Illnesses	X						
Concomitant Medications (inc. glaucoma meds and supp. prednisolone)	X		X	X	X	X	
BCVA (ETDRS at 4m)	X		X	X	X	X	
Visual field mean deviation	X					X	
Ophthalmic Examination (dilated fundus exam)	X		X	X	X	X	
Cataract density grade (scale 1 to 4) and type	X						
Glaucoma type and severity	X						
OCT RNFL & Macula	X					X	
Intraocular Pressure (Goldmann and CATS)	X		X	X	X	X	
Corneal Endothelial Specular Microscopy	X					X	
Gonioscopy	X					X	
Ocular Response Analyzer	X					X	
Pachymeter	X						
Indirect Ophthalmoscope	X					X	
Indicate the incision type, location, and size (mm)		X					
Type of IOL(e.g. monofocal, toric, multifocal, etc.) and lens power	X	X					
Type of MIGS device	X	X					
Record any surgical complications		X					X
Subject reported AEs prior to or after surgery	X		X	X	X	X	X
Intracanalicular dexamethasone insert		X					
Ocular Comfort Index					X	X	
Anterior chamber cell count			X	X	X	X	
Anterior chamber cell flare			X	X	X	X	
Insert Visualization			X	X	X	X	
Prescribe post-operative topical therapy regimen			X				

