5.2.3 Adverse Event Information Collection

The investigator (or designee) will record all AEs that occur during the study The definition of an AE and SAE, and information on the determination of severity and relationship to treatment are provided in Section 7.

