7.2 Recording and Reporting Adverse Events

All AEs and SAEs will be recorded only if they are medically relevant.

All SAEs, regardless of assessment of causal relationship to study insert will be reported to Ocular Therapeutix.

To report an SAE, Ocular Therapeutix will be contacted at the following:

[contact]

SAE [contact]

The investigator will promptly report to the IRB all unanticipated problems involving risks to patients. This includes death from any cause and all SAEs related to the use of the study insert. All SAEs will be reported to the IRB, regardless of assessed causality.

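### The study promises to address elevated IOP directly, but its only endpoint built on IOP readings is a mean at 1 and 3 months, tested with no confidence interval and without the Day 7 reading

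*Combined protocol and SAP*

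**What the plan says.** Section 1.3 says glaucoma surgeons may hold back from the insert because of "concerns regarding safety with respect to elevated intraocular pressure. This prospective study will address those concerns directly". Section 6.1 lists raised IOP with optic nerve damage among the risks of ocular steroids, whether given as drops or insert.

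Section 8.2 has one endpoint defined on IOP readings, the first primary endpoint: "Mean Reduction in IOP at 1 and 3 months as measured by Goldmann Applanation Tonometer and comparison between groups". Two other primary endpoints bear on IOP indirectly: the between-group difference in adverse events, and the number of glaucoma medications at 3 months. No section gives a size of rise, a count of eyes with a rise, or a peak IOP.

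On analysis, section 9 says: "Primary endpoints and secondary endpoints will be analyzed through statistical hypothesis testing". It also plans mean, median and SD for continuous variables, and frequency and percentage for categorical ones. It names no confidence interval, test, alpha or margin.

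On timing, section 4.2.1 describes the insert as designed for "sustained and tapered release of therapeutic levels of dexamethasone to the ocular surface for up to 30 days". Table 1 in section 5.1 schedules Goldmann IOP at baseline, Day 1, Day 7, Day 30 and 3 months. Section 1.5 makes Goldmann the primary IOP measure.

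**The concern.** The safety question is whether some eyes have a pressure rise. A steroid response confined to a few eyes is diluted in an arm mean, so a comparison of means reacts weakly to it. A rise seen at Day 7 that has resolved or been treated by Day 30 does not enter the IOP endpoint at all.

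The remaining route is the adverse-event endpoint. Its definition in section 7.1.1 is broad enough to include a pressure rise, but nothing says how large a rise counts. In an open-label study, two eyes with the same moderate rise could be recorded differently.

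At stake is what a null result would tell the reader. With 20 eyes per arm, a non-significant difference in means is compatible with a difference of several mmHg, and with a few eyes in one arm having large rises. Without an interval or a count, the report would show neither.

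**Working it through.** **Inputs from the documents.** 40 eyes, 20 per arm (section 1.5). Goldmann is the primary IOP measure (section 1.5). Visit windows come from Table 1. A patient who enrols both eyes has one in each arm (section 3.1). The plan gives no sample-size calculation, so there is no stated figure to reproduce.

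**Assumptions.** The documents give no SD for IOP and no size of rise. I use SDs of 3, 4 and 5 mmHg and rises of 10 or 15 mmHg for illustration only. I assume a two-sided 0.05 two-sample t-test, independent eyes and no dropout, because section 9 names no test.

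**Timing.** Day 7 ± 2 is Days 5–9, well inside a release period of up to 30 days. Day 30 ± 7 is Days 23–37. Taking 3 months as Day 90, ± 14 is Days 76–104. The IOP endpoint uses only the last two.

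**Precision of the mean difference.** Half-width = t(0.975, 38) × SD × √(2/20) = 2.024 × 0.3162 × SD = 0.640 SD, or 1.9, 2.6 and 3.2 mmHg for SDs of 3, 4 and 5.

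If every patient gave both eyes (20 pairs) with an assumed within-patient correlation of 0.5, it would be t(0.975, 19) × SD × √(2 × 0.5/20) = 2.093 × 0.2236 × SD = 0.468 SD, or 1.4, 1.9 and 2.3 mmHg. Section 3.1 expects only a few two-eye patients, so the true figure should lie much nearer the first set.

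**Response of the mean test to rises in a few eyes.** A 15 mmHg rise in 2 of 20 insert eyes moves the arm mean by 2 × 15/20 = 1.5 mmHg. Share of simulated trials with p < 0.05 (200,000 per scenario), with the rise present at the visit analysed:

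| Rise; insert vs control eyes affected | SD 3 | SD 4 | SD 5 |
|---|---|---|---|
| 15 mmHg; 2 vs 0 | 9% | 9% | 8% |
| 15 mmHg; 3 vs 0 | 19% | 16% | 14% |
| 15 mmHg; 4 vs 0 | 35% | 28% | 23% |
| 15 mmHg; 3 vs 1 | 2% | 4% | 4–5% |
| 10 mmHg; 2 vs 0 | 8% | 7% | 7% |

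In the first row the affected eyes also inflate the SD, so the average half-width becomes 2.8, 3.3 and 3.8 mmHg. Adding the 1.5 mmHg shift, a typical interval reaches up to 4.3, 4.8 and 5.3 mmHg. A rise present only at Day 7 contributes nothing to any row.

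**What a count would and would not add.** Fisher's two-sided p for 2, 3, 4 and 5 of 20 against 0 of 20 is 0.49, 0.23, 0.11 and 0.047, so as a between-arm test the count is no remedy. The exact (Clopper-Pearson) 95% interval for one arm is 1.2% to 31.7% for 2/20 and 0% to 16.8% for 0/20. These intervals are valid within an arm because no patient contributes two eyes to the same arm.

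**The case against.** The strongest reply is that the plan has other routes. Section 7.1.1 counts any unfavorable sign, and any clinically significant worsening of an existing condition, as an adverse event. Section 6.2 has risks monitored at every follow-up visit, and the adverse-event difference is a primary endpoint. A 15 mmHg rise in a glaucomatous eye is the kind least likely to go unrecorded. That stands. A reader might infer that the plan would miss large rises altogether, and the documents do not support it. The gap lies mainly with moderate or transient rises, for which no criterion exists. The medication count is taken only at 3 months and shows neither when nor how far pressure rose.

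Section 9 also plans descriptive statistics. If these are applied to IOP, the 2-of-20 example would show a typical insert-arm SD of about 5.5, 6.0 or 6.7 against 3, 4 or 5 in controls, and a reader could build an unpaired interval from mean, SD and n. This too stands, and it lessens the loss. It does not commit the sponsor to an interval, or to one that allows for paired eyes.

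Four stronger readings go too far:
- That the sponsor will treat a non-significant result as proof of similar safety. Section 1.2 thinks similar safety plausible, but that is background; no section sets such a rule.
- That the endpoint misses the release period entirely. Days 23–37 overlap its end.
- That the documents contradict themselves on when IOP is analysed. Section 3.1 says "At Day 1, Day 7, Day 30, and Day 90, primary and secondary endpoints will be assessed alongside standard-of-care procedures", but this is a general visit summary. The synopsis, section 1.5 and section 8.2 all give 1 and 3 months.
- That the adverse-event recording rules belong to this point. Section 5.2.3 says "The investigator (or designee) will record all AEs that occur during the study", and section 7.2 says "All AEs and SAEs will be recorded only if they are medically relevant". These must be reconciled, but as a separate matter.

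**Conclusion.** The point holds in a limited form. The trial sets out to address elevated IOP directly, yet the only endpoint built on IOP readings is a mean at two visits, tested without a planned interval, and the Day 7 reading feeds no IOP endpoint. Under the assumptions above, the mean test picks up a 15 mmHg rise in 2 of 20 insert eyes in about 8% to 9% of trials, little above its 5% false-positive rate. The half-width of 0.64 SD (1.9 to 3.2 mmHg) assumes independent eyes and no dropout. It would be somewhat narrower if some patients contribute both eyes, and wider with losses.

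The detection figures describe the test of means alone, not the plan's overall chance of noticing a problem, since adverse events are a second route. The SDs and rises are illustrative, but the conclusion is the same across the range tried for two or three affected eyes against none. The trial can run as written, but its own safety question would be only partly answered. The change should be made before analysis.

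**What to change.** 1. **Section 9.** Report the baseline-adjusted between-arm difference in Goldmann IOP at 1 and 3 months with its 95% CI, using a method that allows for patients who contribute both eyes. State that a non-significant difference will not be interpreted as similar safety.
2. **Section 8.2.** Add a descriptive safety endpoint: the number and proportion of eyes per arm with a Goldmann rise above baseline, of a size the sponsor fixes in advance, at any scheduled postoperative visit including Day 7. State whether Day 1 counts and which eyes form the denominator. Give an exact 95% CI per arm, and show the result alongside change in IOP-lowering medications, so that a rise masked by added drops, or one seen on fewer drops, is visible.

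**Cost.** Wording and analysis only; Goldmann and medication data are already scheduled in Table 1. Baseline adjustment helps a little. At an assumed baseline correlation of 0.5 with equal variances, the SD of change equals the SD of IOP, and the half-width is t(0.975, 37) × √(2/20) × √(1 − 0.25) = 2.026 × 0.3162 × 0.866 = 0.555 SD, or 1.7, 2.2 and 2.8 mmHg.

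**Downside.** The count is imprecise (0/20 still allows up to 16.8%) and adds no between-arm power. If the pre-stated rise is small, it will also count ordinary variation. The conclusion will be more modest. The gain is that affected eyes and the remaining uncertainty are shown.
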